### **8.2.3. Allowable Medications**

Other concomitant medication must be stable for 2 weeks prior to screening and, if possible, not be adjusted during the study except for reasons of safety.

The following must be stable for a minimum of 6 weeks prior to randomization:

- Postmenopausal hormone therapy
- Thyroid hormone supplements
- Fibrates (excluding gemfibrozil)

The following must be stable for: a minimum of 4 weeks prior to screening:

- Hypertriglyceridemia therapy
- Lipid-lowering therapy, including dietary supplements and herbal remedies used for the purposes of lipid lowering
- Diabetes medications

The following must be stable for a minimum of 3 months prior to screening and, if possible not be adjusted during the study except for reasons of safety:

- Antiobesity medications

*The following may not be taken within 4 weeks of Screening (Week -2, Visit S1), but may be initiated beginning at Week 24 if LDL-C threshold criteria have been met and it is needed as adjunctive LDL-C-lowering therapy.*

- *Alirocumab (Praluent®)*
- *Evolocumab (Repatha®)*

### **8.3. Treatment Compliance**

#### Screening Compliance

No study medication treatment will be given during the Screening period; therefore, compliance will not be assessed.

#### Treatment Period Compliance

At each patient visit during the treatment period, designated clinical site staff will assess patient IMP intake compliance by counting the number of tablets that are returned as unused and by querying the patient with regards to daily intake. If the patient has not taken all doses of study drug as instructed, the patient will be queried for a reason, findings will be documented, and the patient will be counseled on the importance of carefully following all dosing instructions. Factors contributing to poor compliance will be determined and, if possible, remedied. Patients demonstrating poor compliance will continue to be counseled on the importance of carefully following all dosing instructions, but will not be removed from the study.

### **8.4. Blinding**

At Week 0 (Visit T1), patients who satisfy all entry criteria during the screening period will be randomized to a treatment group. The Investigator or designee will contact IWRS at this visit to randomize the patient into the study. The IWRS will determine the randomized treatment assignment based on their HeFH status and baseline statin dose and assign a randomization number and the appropriate study drug container via medication identification numbers (MED ID). A patient is considered to be randomized when they have been assigned a randomization number by IWRS.

After patients have been randomized, study drug, which is assigned by the IWRS, will be administered in a double-blind fashion. The Sponsor, all clinical site personnel (Investigator, pharmacist, etc), and other vendor personnel will be blinded to the treatment group for each patient. Patients will also be blinded to the treatment they receive. Unblinded User(s) will be designated for each clinical site and at the sponsor (or designee) as needed. [REDACTED] will provide these unblinded individuals with IWRS access allowing them the ability to perform emergency unblinding of treatment for an individual patient. An affirmative entry of the user's login details will be required before the treatment group is displayed. Unblinding at the clinical site for any other reason will be considered a protocol deviation. Unblinded treatments for patients will NOT automatically discontinue the patient from the study. To discontinue the patient from the study, the appropriate clinical site personnel will need to register the 'discontinuation' visit separately.

Blinding of treatment must be maintained for all patients unless, in the opinion of the Investigator, the safety of the patient may be at risk. Only under the rarest of circumstances

should the Investigator consider breaking the blind and only when medical/supportive care cannot be provided without determining if the patient is receiving active drug treatment. In the event that the blind needs to be broken prior to completion of the study, the Investigator should contact the appropriate Medical Monitor by telephone. If the blind must be broken prior to consultation with the Medical Monitor, contact must be made within 24 hours of breaking the blind. At the initiation of the study, the clinical site will be instructed on procedures for breaking the blind via the IWRs. In all cases of breaking the blind, the Investigator must document in the patient's medical record the date, time, and reason for breaking the blind, and the names of personnel involved.

Limited vendors (ie, the bioanalytical laboratory and other vendor personnel, if any, that are responsible for PK analysis) will have access to the randomization codes to facilitate PK analytical work, and will be instructed to not communicate in any manner information associated with treatment assignment to any personnel at the clinical site, the Sponsor, [REDACTED].

Postrandomization values for individual laboratory measures for LDL-C, TG, TC, HDL-C, non-HDL, apoB, and hs-CRP, including any plasma concentration of ETC-1002 and its metabolite, that may inadvertently suggest treatment assignment will not be available to personnel from the clinical site, the patient, the Sponsor, [REDACTED].

An independent blinded expert CEC will adjudicate all *clinical endpoints*, including death, using standardized definitions. *Clinical endpoints will also be reported as SAEs.* Additional details and definitions will be provided in a CEC Charter.

An independent DMC will monitor unblinded accumulating patient safety *and efficacy* data until the last patient has completed study treatment. In addition, data on SAEs and deaths will be monitored by the DMC during this period. At each DMC review, relevant unblinded safety *and efficacy* information from ongoing studies will be provided to the DMC by an independent, unblinded [REDACTED] programmer and statistician. Additional details will be provided in a DMC Charter.

## **8.5. Overdose**

*There is no specific antidote for an overdose of bempedoic acid. Management of an overdose should be focused on the treatment of symptoms. These symptoms should be managed according to current standards of care with appropriate supportive measures. Also discontinuation of study drug should be considered.*

## **9. INVESTIGATIONAL MEDICINAL PRODUCT**

### **9.1. Investigational Medicinal Product Supply and Control**

The Sponsor will supply the IMP for this study. The IMP for this study includes ETC-1002 (180-mg film-coated tablets) and matching placebo (film-coated tablets). IMP will be distributed and released in accordance with regional and local requirements during the conduct of the study.

The MED ID number (an identifier on the study drug packaging) will be obtained via IWRs and used to select double-blind IMP from available clinical supplies at the clinical site.

Double-blind IMP will be dispensed in 100 day supply increments (one 100-day supply bottle) to patients by appropriate clinical site personnel at Week 0 (Visit T1), Week 12 (Visit T4), and Week 24 (Visit T5). Double-blind IMP will be dispensed in 35-day supply increments (2 bottles; one 100-day supply bottle and one 35-day supply bottle) to patients at Week 36 (Visit T6).

Please see Pharmacy Manual for detailed storage requirements and management instructions.

### **9.2. Administration of Investigational Medicinal Product**

Patients will be instructed to ingest IMP orally once daily (*once every 24 hours*) at *approximately the same time each day* with water. *IMP may be taken* with or without food. On clinic visit days, patients will be instructed to delay ingestion of IMP until all study procedures have been completed. If a patient arrives at clinic on Visits T4, T5, or T7 without having fasted or having taken IMP before arriving at the clinic, reschedule the visit (the next day or as soon as possible) so that the fasting and dosing requirements have been met. Patients will be instructed to return all packaging and unused IMP at each clinic visit.

If the patient forgets to take IMP in the morning on nonclinic visit days, it may be taken up to 12 hours later the same day. After that time, the patient should not take IMP that day and should resume ingestion of IMP the following morning. Details describing the reasons for nondosing should be documented in the patient's medical records and eCRF. Extra IMP (7 extra days per bottle) is provided and can be used, if needed, prior to the next visit or to replace a dose of IMP that cannot be used because it is lost or damaged.

### **9.3. Investigational Medicinal Product Accountability**

Accurate records of the receipt of all IMP shipped by the Sponsor (or designee) and the disposition of that IMP must be maintained.

IMP records or logs must comply with applicable regulations, local law, and guidelines, and should include:

- Amount received/placed in storage area
- Amount currently in storage area
- MED ID number for all IMP

- Dates and initials of person(s) responsible for IMP inventory (including entry/movement/disposition)
- Date and amount of IMP dispensed to each patient, including unique patient identifiers
- Date that IMP was returned by patient, assessment of compliance, and relevant documentation of discrepancies
- Nonstudy disposition (eg, lost, broken, wasted)
- Amount returned to Sponsor/Sponsor's designee/destroyed or amount destroyed per local standard operating procedure (SOP) following accountability by site monitor.

#### **9.4. Investigational Medicinal Product Handling and Disposal**

Upon completion or termination of the study, all used and unused IMP with the IMP packaging must be returned to the Sponsor (or designee) for eventual destruction unless otherwise authorized by the Sponsor. All IMP returns must be accompanied by the appropriate documentation.

## 10. STUDY PROCEDURES

### 10.1. Informed Consent

The patient must be adequately informed of the nature and risks of the study and understand the informed consent document (ICD). No study-related procedure will be performed until the patient has been completely informed of the study, has freely consented to take part in the study, and has signed and dated an ICD approved by the Sponsor (or designee) and the IRB or IEC. Participation in banking of samples for genetic analysis is optional for all patients, and consent for this must be documented in the patient's written informed consent.

### 10.2. Procedures and Schedule of Assessments

Patients who provide informed consent and sign the ICD will be eligible to begin screening for the study. The study is comprised of 2 distinct periods: screening and double-blind treatment.

The schedule of study events is provided in [Appendix 1](#). However, a patient can be seen at any time for reasons of safety.

Data will be captured on eCRFs. Randomization, drug supply (re)ordering, and patient tracking will occur via IWRS. Instructions for these systems will be provided separately.

#### 10.2.1. Screening Week -2 (Visit S1; Days -16 to -4)

The screening period will begin with a screening visit that will occur 2 weeks prior to randomization. Visit S1 will allow the Investigator to assess the patient's preliminary eligibility. After the patient provides written informed consent (see Section 10.1), the patient will undergo the following assessments and procedures at Visit S1:

- Demographics
- Clinically relevant medical history, including assessment of HeFH status and ASCVD
- Concomitant and prohibited medication review
- Height (cm), weight (kg), BMI
- Vital signs
- Clinical laboratory evaluations:
  - Hematology, blood chemistry, coagulation, and urinalysis
  - Basic fasting lipids (TC, calculated LDL-C, HDL-C, non-HDL-C, and TG)
  - HbA1C
  - TSH
  - *FSH (in appropriate female patients)*
  - Serum pregnancy test (on appropriate female patients)

- Serology (including HBsAg, HCV)
- Review of all inclusion/exclusion criteria that can be assessed at this time
- Conduct diet and exercise counseling
- Contact IWRS to register the patient

Patients who meet all enrollment criteria that can be assessed at Visit S1 will be instructed to continue their therapy(s) for lipid regulation and to maintain consistent diet and exercise patterns throughout the study. Patients who fail to meet any entry criterion that can be assessed at Visit S1 are considered to be screen failures and are not required to return for additional visits (although a patient can be seen at any time for safety reasons).

Note:

- An optional visit approximately 1 week later MAY be completed if patient fails to meet a lipid entry criterion. If this optional visit is completed, the mean of lipid values from both visits will be used to determine eligibility.
- *An optional visit between Visits S1 and T1 may be scheduled to collect screening fasting labs in the event that the patient arrives at Visit S1 in a nonfasted state.*
- An optional visit between Visits S1 and T1 may be completed if the patient's DBP and/or SBP meet the exclusion criteria levels. Patients may randomize after blood pressure medications have been adjusted, they have been on stable doses of blood pressure medications for at least 2 weeks, and the repeat blood pressure values (DBP and/or SBP) no longer meet exclusionary values.
- An optional visit between Visits S1 and T1 may be completed to determine eligibility if the patient's eGFR, ALT, AST, and/or TB meet exclusion criteria levels. If this optional visit is completed, the repeated value will be used to determine eligibility.
- Patients who are considered to be screen failures due to not meeting stability requirements for a condition or concurrent medication may be considered for rescreening after consultation with the Sponsor (or designee). These patients must be re-consented, re-registered in the IWRS, and will have a new patient ID number assigned.

#### **10.2.2. Treatment Week 0 (Visit T1; Day 1)**

Prior to scheduling Visit T1, review the screening clinical results to evaluate whether the patient continues to meet eligibility criteria.

- If the patient meets eligibility criteria, then schedule the Visit T1 and proceed with the Visit T1 procedures

If the patient has met all inclusion criteria and none of the exclusion criteria, the patient may be randomized into the double-blind treatment period. Patients who fail to meet any entry criterion prior to randomization are considered to be screen failures, will not be randomized into a treatment group, and are not required to return for additional visits. Patients are considered randomized once all eligibility criteria are confirmed and a randomization number is obtained by the IWRS on the day of first dose.

The patient will undergo the following assessments and procedures at (Visit T1)

- Concomitant and prohibited medication review (ongoing)
- Assess AEs (starting from signing of the informed consent document)
- Physical examination (PE)
- Weight
- 12-Lead electrocardiogram (ECG)
- Vital signs
- Clinical laboratory evaluations:
  - Hematology, blood chemistry, and urinalysis

*Note: Urine pregnancy test (for females of childbearing potential)*

- Basic fasting lipids (TC, calculated LDL-C, HDL-C, non-HDL-C, and TG)
- apoB
- HbA1C
- hs-CRP
- Reserve sample
- *Genetic sample (if the patient has consented to provide a genetic sample)*

- Review inclusion/exclusion criteria to establish patient eligibility
- Conduct diet and exercise counseling
- IWRS contact to obtain the patient randomization number and MED ID number for double-blind study drug
- Dispense IMP and provide dosing instructions
- Schedule next visit

#### **10.2.3. Treatment Week 4 (Visit T2; ± 3 days)**

If the patient is withdrawing early from the study at this visit, proceed to [Section 10.2.8](#) for the list of the required assessments.

If the patient is withdrawing from IMP treatment at this visit, proceed to [Section 10.2.8](#) for the list of the required assessments. The patient will be asked to continue to be followed for safety using the protocol-specified visit schedule. If the patient consents for follow-up, schedule the next protocol-specified visit.

Patients who do not provide consent to continue to return to the clinic for safety assessments after withdrawing from IMP treatment will be asked to participate in phone calls from the site at protocol-specified visits, or at a minimum at 52 weeks, to inquire about the patient's current health status and collect information on AEs (eg, recent procedures, hospitalizations, and if the

patient has died, the cause of death). If the patient consents for telephone contacts, schedule the next protocol-specified visit.

Patients will undergo the following assessments and procedures at Week 4 (Visit T2):

- Concomitant and prohibited medication review (ongoing)
- Assess AEs, including muscle-related AEs (ongoing)
- Weight
- Vital signs
- Clinical laboratory evaluations:
  - Hematology, blood chemistry, and urinalysis
  - Basic fasting lipids (TC, calculated LDL-C, HDL-C, non-HDL-C, and TG)
- Conduct diet and exercise counseling
- Return of IMP; assessment and recording of IMP compliance
- Return IMP container from Visit T1 to patient for continued dosing and provide dosing instruction
- Schedule next visit

*Note: If this visit is being conducted at the site for patients who have consented to be followed for safety assessments, including basic fasting lipids, after withdrawing from IMP treatment, all assessments except for those procedures pertaining to IMP management (IMP dispensing, IMP compliance, IMP accountability) should be completed.*

*Note: If this visit is being conducted by telephone contact for patients who have consented to be followed by phone for safety assessments after withdrawing from IMP treatment, collect information as reported by the patient regarding AEs, concomitant medication, and current health status.*

#### **10.2.4. Treatment Week 8 (Visit T3; ± 3 days)**

If the patient is withdrawing early from the study at this visit, proceed to [Section 10.2.8](#) for the list of the required assessments.

If the patient is withdrawing from IMP treatment at this visit, proceed to [Section 10.2.8](#) for the list of the required assessments. The patient will be asked to continue to be followed for safety using the protocol-specified visit schedule. If the patient consents for follow-up, schedule the next protocol-specified visit.

Patients who do not provide consent to continue to return to the clinic for safety assessments after withdrawing from IMP treatment will be asked to participate in phone calls from the site at protocol-specified visits, or at a minimum at 52 weeks, to inquire about the patient's current health status and collect information on AEs (eg, recent procedures, hospitalizations, and if the patient has died, the cause of death). If the patient consents for telephone contacts, schedule the next protocol-specified visit.

- Patients will undergo the following assessments and procedures at Week 8 (Visit T3):
- Concomitant and prohibited medication review (ongoing)
- Assess AEs, including muscle-related AEs (ongoing)
- Weight
- Vital signs
- Clinical laboratory evaluations:
  - Hematology, blood chemistry, and urinalysis
  - Basic fasting lipids (TC, calculated LDL-C, HDL-C, non-HDL-C, and TG)
- Conduct diet and exercise counseling
- Return of IMP; assessment and recording of IMP compliance
- Return IMP container from Visit T1 to patient for continued dosing and provide dosing instruction
- Schedule next visit

Note: If this visit is being conducted at the site for patients who have consented to be followed for safety assessments, *including basic fasting lipids*, after withdrawing from IMP treatment, all assessments except for those procedures pertaining to IMP management (IMP dispensing, IMP compliance, IMP accountability) should be completed.

Note: If this visit is being conducted by telephone contact for patients who have consented to be followed by phone for safety assessments after withdrawing from IMP treatment, collect information as reported by the patient regarding AEs, *concomitant medications*, and current health status.

#### **10.2.5. Treatment Week 12 (Visit T4; ± 3 days)**

If the patient is withdrawing early from the study at this visit, proceed to [Section 10.2.8](#) for the list of the required assessments.

If the patient is withdrawing from IMP treatment at this visit, proceed to Section 10.2.8 for the list of the required assessments. The patient will be asked to continue to be followed for safety using the protocol-specified visit schedule. If the patient consents for follow-up, schedule the next protocol-specified visit.

Patients who do not provide consent to continue to return to the clinic for safety assessments after withdrawing from IMP treatment will be asked to participate in phone calls from the site at

protocol-specified visits, or at a minimum at 52 weeks, to inquire about the patient's current health status and collect information on AEs (eg, recent procedures, hospitalizations, and if the patient has died, the cause of death). If the patient consents for telephone contacts, schedule the next protocol-specified visit.

Patients will undergo the following assessments and procedures at Week 12 (Visit T4):

- Concomitant and prohibited medication review (ongoing)
- Assess AEs, including muscle-related AEs (ongoing)
- Weight
- Vital signs
- Clinical laboratory evaluations:
  - Hematology, blood chemistry, and urinalysis
  - Basic fasting lipids (TC, calculated LDL-C, HDL-C, non-HDL-C, and TG)
  - apoB
  - HbA1C
  - hs-CRP
  - PK sample (*patients randomized after Protocol Amendment 3 and subsequent amendments are excluded from PK sampling*)
  - Reserve sample
- Conduct diet and exercise counseling
- Return of IMP; assessment and recording of IMP compliance
- IWRS contact to obtain the MED ID number for IMP
- Dispense IMP
- Schedule next visit

Note: If this visit is being conducted at the site for patients who have consented to be followed for safety assessments, *including basic fasting lipids*, after withdrawing from IMP treatment, all assessments except for those procedures pertaining to apoB, hs-CRP, PK samples, reserve samples, and IMP management (IMP dispensing, IMP compliance, IMP accountability) should be completed.

Note: If this visit is being conducted by telephone contact for patients who have consented to be followed by phone for safety assessments after withdrawing from IMP treatment, collect information as reported by the patient regarding AEs, *concomitant medications*, and current health status.

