#### **10.2.8. Treatment Week 52 (Visit T7; ± 7 days)**

Patients will undergo the following assessments and procedures at Week 52 (Visit T7), when completing an End of Study (EOS) visit, withdrawing from study (early withdrawal), or withdrawing from IMP treatment:

Patients will undergo the following assessments and procedures at Week 52 (Visit T7):

- Concomitant and prohibited medication review (ongoing)
- Assess AEs, including muscle-related AEs (ongoing)
- PE
- Weight
- 12-Lead ECG
- Vital signs
- Clinical laboratory evaluations:
  - Hematology, blood chemistry, and urinalysis
  - Basic fasting lipids (TC, calculated LDL-C, HDL-C, non-HDL-C, and TG)
  - apoB
  - HbA1C
  - hs-CRP
  - PK sample (*patients randomized after Protocol Amendment 3 and subsequent amendments are excluded from PK sampling*)
  - Reserve sample
- Return of IMP; assessment and recording of IMP compliance
- Complete study status in IWRS (ie, early withdrawal or completed study)
- *Review and offer the open-label extension study (Study 1002-050) to the patient*

Note: For patients who withdraw from IMP treatment:

- *Capture the reason for withdrawing from IMP treatment and record on the eCRF*
- Determine whether the patient will or will not consent for follow-up visits through study completion
- If the patient provides consent to continue to be followed for safety assessments per the protocol visit schedule, schedule follow-up visits as they would have occurred if the patient were continuing in the study and complete the visit required procedures listed in the appropriate visit specific section within **Section 10** and **Appendix 1**. No further IMP will be dispensed for patients who withdraw from IMP treatment.
- If the patient does not provide consent to be followed for safety assessments per the protocol (either by returning to clinic or by phone), this visit (Visit T7) will be considered the EOS/Early Withdrawal from study visit and no further visits will be scheduled.

Note: If this visit is being conducted at the site for patients who have consented to be followed for safety assessments, *including basic fasting lipids*, after withdrawing from

IMP treatment, all assessments except for those procedures pertaining to apoB, hs-CRP, PK samples, reserve samples, and IMP (IMP dispensing, IMP compliance, IMP accountability) management should be completed.

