NOTE: For patients who withdraw from IMP treatment, but consent to be followed for safety assessments and return to clinic for these visit, the visits will occur according to the protocol schedule. Safety assessments should include clinical safety and basic lipid laboratories (except for apoB and hs-CRP), adverse events, PE, vital signs, and ECGs. For patients who withdraw from IMP treatment, but consent to be followed for safety assessments by phone, the telephone contacts will occur according the protocol schedule with information regarding current health status and to collect information on AEs (eg, recent procedures, hospitalizations, and if the patient has died, the cause of death). If a patient does not provide consent to be followed for safety assessments per the protocol (either by returning to clinic or by phone), Visit T7 will be considered the EOS/Early Withdrawal from study and no further visits will be scheduled.

 An optional visit approximately 1 week later MAY be completed if patient fails to meet a lipid entry criterion. If this optional visit is completed, the mean of lipid values from both visits will be used to determine eligibility.

 An optional visit between Visits S1 and T1 may be completed if the patient's DBP and/or SBP meet the exclusion criteria levels. Patients may randomize after blood pressure medications have been adjusted, the patients have been on stable doses of blood pressure medications for at least 2 weeks, and the repeat blood pressure values (DBP and/or SBP) do not meet exclusionary values. An optional visit between Visit S1 and T1 may be completed to determine eligibility if the patient's eGFR, ALT, AST, and/or TB meet exclusion criteria levels. If this optional visit is completed, the repeated value will be used to determine eligibility.

 All procedures will be completed for all patients at either End of Study (EOS) if completing the study or early withdrawal.

 Body weight will be measured in the morning while fasting, using consistent scales, after voiding, and without shoes and outerwear (eg, coats).

 Single 12-lead ECG will be collected prior to any blood sample collection.

 Vital signs will include DBP, SBP, and HR and will be collected prior to any blood sample collection. Patient will rest for 5 minutes prior to assessments

 Serology for HBsAg, HCV

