5.2.1.2 Full Analysis Set (FAS)

The Full Analysis Set (FAS) is defined as all randomized patients and is also known as the intention-to-treat (ITT) set of patients. FAS will be used for all efficacy analyses. In addition, FAS will be also used for summary for disposition, demographics, and baseline characteristics. Patients in the FAS will be included in their randomized treatment group.

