5.3 Primary Efficacy Endpoints and Analyses

For all efficacy analyses, the FAS will be used, with patients included in their randomized group, regardless of the treatment they actually received.

The primary and key secondary efficacy endpoints will be included in a step-down testing procedure to control overall type I error. Below endpoints will be tested sequentially at alpha level of 0.05. Each endpoint will be tested only if the previous endpoint achieved statistical significance.

1. percent change from baseline to Week 12 in LDL-C (primary efficacy)
2. percent change from baseline to Week 24 in LDL-C
3. percent change from baseline to Week 12 in non-HDL-C
4. percent change from baseline to Week 12 in TC
5. percent change from baseline to Week 12 in apoB
6. percent change from baseline to Week 12 in hsCRP

The clinical hypothesis being tested for each respective endpoint is that a treatment regimen with bempedoic acid 180mg daily in addition to other lipid modifying therapies (including statin) will result in higher reduction in respective lipid value than that from the lipid modifying therapy alone.

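### apoB and hs-CRP are not drawn at clinic follow-up after IMP withdrawal, although their Week 12 changes are step-down endpoints 5 and 6 in all randomised patients

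*Protocol*

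**What the plan says.** **Collection.** For a patient who has stopped IMP but agrees to clinic follow-up, Protocol 10.2.5 (Week 12) requires "all assessments except for those procedures pertaining to apoB, hs-CRP, PK samples, reserve samples, and IMP management". Basic fasting lipids remain in. Protocol 10.2.6 (Week 24) and 10.2.8 (Week 52) carry the same exception. The note to Protocol Appendix 1 repeats it: "Safety assessments should include clinical safety and basic lipid laboratories (except for apoB and hs-CRP), adverse events, PE, vital signs, and ECGs". The note to SAP Appendix 1 does the same.

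**The one off-schedule draw.** The Protocol 10.2.8 assessments, which include apoB and hs-CRP, are also done "when completing an End of Study (EOS) visit, withdrawing from study (early withdrawal), or withdrawing from IMP treatment". A patient therefore has both markers measured once, at the visit where IMP is withdrawn.

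**Role in the analysis.** SAP 5.3 lists six step-down endpoints: "Below endpoints will be tested sequentially at alpha level of 0.05". The fifth is "percent change from baseline to Week 12 in apoB" and the sixth is "percent change from baseline to Week 12 in hsCRP". Under SAP 5.2.1.2, "FAS will be used for all efficacy analyses", and that set is everyone randomised, in the assigned group.

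**Missing data.** SAP 5.3.2 imputes missing step-down values. Patients whose last dose was more than 7 days before the Week 12 visit are imputed from placebo patients only. Those still on drug are imputed with treatment group in the model. SAP 5.3.3 analyses apoB and hs-CRP at Weeks 24 and 52 on observed data. SAP 5.3.4 adds observed-case (FAS) and on-treatment (SP, to 7 days after last dose) sensitivity analyses.

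**The concern.** An all-randomised analysis depends on what happens to patients after they stop drug, and the usual protection is to keep measuring them. The protocol does this for the three lipids that supply endpoints 1 to 4. It does not do so for apoB and hs-CRP, although the patient attends and gives fasting blood at the same visit. Within one hierarchy, the off-drug part of endpoints 1 to 4 can be observed, while that of endpoints 5 and 6 is mostly assumed.

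The sensitivity analyses do not close the gap. With almost no off-drug apoB or hs-CRP values in the database, the FAS observed-case analysis and the on-treatment analysis use nearly the same records. Agreement between them would say little about the imputation. At Weeks 24 and 52 there is no imputation, so most off-drug patients leave the analysis.

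**Working it through.** **1. The plan's exposure figures (SAP 4.4).** Inputs: 1300 and 650 randomised; dropout 7.5% at 6 months and 10.0% at 12 months in each group. Expected exposed = N × (1 − dropout):
- ETC-1002: 1300 × 0.925 = 1202.5 (printed 1,202); 1300 × 0.90 = 1170 (printed 1,170)
- Placebo: 650 × 0.925 = 601.25 (printed 601); 650 × 0.90 = 585 (printed 585)

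The figures reproduce. The plan uses these rates to count patients still exposed, so I read them as rates of stopping IMP.

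**2. Patients off IMP by Week 12.** No rate is given, so this is an assumption with a range.
- Even accrual of 7.5% over 26 weeks: 0.075 × 12/26 = 3.46%; 1300 × 0.0346 = 45.0, 650 × 0.0346 = 22.5, total 67.5, or about 68
- Low, 2%: 26 + 13 = 39
- High, the full 6-month rate, 7.5%: 97.5 + 48.75 = 146.25, or about 146

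For values that could be recovered, these are upper bounds. Patients followed by telephone, or not at all, give no blood, and their LDL-C is missing too.

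**3. When the withdrawal draw counts.** The SAP 5.1 window for Week 12 is study days 72 to 127. A withdrawal draw in that window can serve as the Week 12 value; an earlier one cannot. Similarly, a withdrawal draw counts for Week 24 only on days 128 to 211, and for Week 52 only from day 310.

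**4. Effect on the estimates.** Suppose there is no drug effect once off drug, and a fraction d is off drug in each arm. The all-randomised mean effect is then (1 − d) times the on-drug effect.
- *Week 12 main analysis.* Placebo-based imputation reproduces about (1 − d). At d = 3.46% this is 0.965, an attenuation of about 3.5%.
- *Analyses without off-drug values.* These estimate the on-drug effect and overstate the all-randomised effect by 1/(1 − d).

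| Time point | d | Patients off IMP | 1/(1 − d) |
|---|---|---|---|
| Week 12, observed-case sensitivity | 3.46% | about 68 | 1.036 |
| Week 24, observed data | 7.5% | 97.5 + 48.75, about 146 | 1.08 |
| Week 52, observed data | 10% | 130 + 65 = 195 | 1.11 |

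The factors take every off-drug value as absent, so draws that fall in a window lower them slightly. They describe a difference in means, so they fit apoB. For hs-CRP, analysed by Wilcoxon and Hodges-Lehmann, they are only indicative.

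**The case against.** The strongest reply is that SAP 5.3.2 already handles the gap where it matters for error control. Only the Week 12 values of these markers are in the hierarchy. Imputing off-drug patients from placebo pulls the effect toward zero, so it does not favour the drug. These are the last two of six steps: the fifth gates only the sixth, and the sixth gates nothing. The primary objective is safety, and both markers are tertiary objectives. The assumption also has an indirect check, because off-drug LDL-C, non-HDL-C and TC in patients who attend show whether lipids return to placebo level.

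All of this stands, and it limits the point to a modest one. Three stronger readings are tempting but not supported:
- *Every off-drug value is missing by rule.* This is not so. The withdrawal visit includes both markers, and patients who decline clinic visits are missing because they do not attend.
- *Endpoints 5 and 6 target a different estimand from endpoints 1 to 4.* All six share the FAS, the as-randomised rule and the same missing-data rule. What differs is how much of the off-drug data is observed and how much is assumed.
- *The Week 12 result is biased toward the drug.* The imputation works in the other direction.

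What the reply does not remove is that the assumption cannot be tested directly on these two markers, and that Weeks 24 and 52 have no imputation. Return of LDL-C to placebo level is also weak evidence for hs-CRP, which is not a lipid. The SAP does not say how Wilcoxon and Hodges-Lehmann results are combined across imputations, so reliance on imputation is least specified for hs-CRP.

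**Conclusion.** The point holds as a gap between collection and analysis. Two alpha-controlled endpoints in all randomised patients are not measured at off-drug follow-up visits where fasting blood is taken anyway.

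The Week 12 effect is small: at most about 39 to 146 of 1950 patients, about 68 with even accrual, and fewer once non-attenders are removed. At Weeks 24 and 52, outside the hierarchy, overstatement of about 1.08 and 1.11 is possible. These sizes rest on planned dropout, equal rates in both arms and no off-drug effect. The SAP summary of changes records that patients on simvastatin 40 mg/day or higher were withdrawn from study treatment at Amendment 5. Their number is not given, so actual discontinuation may exceed the planned rates. Nothing here shows that a conclusion of the trial would change. The change is worth making because it replaces an assumption with data at low cost.

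**What to change.** Remove apoB and hs-CRP from the off-IMP exception in Protocol 10.2.5 (T4), 10.2.6 (T5) and 10.2.8 (T7), and from the notes to Protocol Appendix 1 and SAP Appendix 1. Use the observed off-drug values in the FAS analyses at Weeks 12, 24 and 52. Keep the placebo-based imputation at Week 12 for off-drug patients who do not attend.

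The cost is two more assays per off-IMP clinic visit, plus an amendment that Protocol 17.3 says needs IRB/IEC approval first. Blood is already drawn at these visits, so no separate visit is needed. Tube requirements are left to the Clinical Laboratory Manual and should be checked.

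If collection can no longer be changed, the SAP should say that off-drug Week 12 values of these markers are imputed except where a withdrawal draw falls in the window. It should add a sensitivity analysis that varies the placebo-based assumption, and state how hs-CRP results are combined across imputations. This needs no new sampling, but it leaves the assumption unobserved.
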